2.3 Treatment comparisons

Eligible individuals who have provided and consent will be allocated to tecovirimat or placebo using a minimised randomisation program that helps maximise balance between the allocated treatment groups with respect to important prognostic variables (including age [<18 , ≥ 18 - <40 , ≥ 40], sex at birth [male/female], previous orthopoxvirus vaccination [yes/no/not known], severity [localised vs disseminated rash (defined as >1 area, e.g. groin & head)], and days since lesion onset [≤ 7 days or >7 days]).

Randomised participants will be issued with a supply of tecovirimat capsules (200mg) or placebo capsules to be taken orally with food as follows:

- Adults aged 18 years or older: three capsules twice a day for 14 days (total daily tecovirimat dose: 1200 mg)
- Children and adolescents aged <18 years:
 - Estimated body weight ≥ 13 to <25 kg: one capsule twice a day for 14 days (total daily tecovirimat dose: 400 mg).
 - Estimated body weight ≥ 25 to <40 kg: two capsules twice a day for 14 days (total daily tecovirimat dose: 800 mg).
 - Estimated body weight ≥ 40 kg: three capsules twice a day for 14 days (total daily tecovirimat dose: 1200 mg).

Although PK/PD modelling suggest that higher doses may be preferable in adult patients weighing ≥ 120 kg, all adults allocated to active tecovirimat will receive the current standard dose (as above) without adjustment for weight.

2.4 Study endpoints

2.4.1 Primary endpoint

- (i) **Time (days) to active lesion resolution**, defined as the first day on which all skin lesions are scabbed or desquamated (and mucosal lesions healed), up to 28 days after randomisation.

2.4.2 Secondary endpoints

- (i) **Time (days) to complete lesion resolution**, defined as the first day on which all lesions are completely resolved (all scabs dropped off and intact skin remains underneath, and mucosal lesions healed), up to 28 days after randomisation.

- (ii) **Time to negative throat swab viral culture**, defined as time to consistently negative culture for monkeypox virus on throat swab at Days 7, 14, 21, and 28.*
- (iii) **Time to negative skin or mucosa swab viral culture**, defined as time to consistently negative culture for monkeypox virus on swab of most recent active skin or mucosa lesion at Days 7, 14, 21, and 28.

2.4.3 Subsidiary outcomes

To evaluate the efficacy of tecovirimat versus placebo in patients with mpox:

- (i) **Clinical status** on day 7, 14, 21 and 28 according to an ordinal scale. The ordinal scale is a) all lesions completely resolved (all scabs dropped off and intact skin remains underneath, and all mucosal lesions healed), b) active lesions resolved (all skin lesions scabbed or desquamated, but not fully resolved), c) active lesions persist but no new lesions in last 24 hours, d) new active lesion(s) in last 24 hours.
- (ii) **Throat swab monkeypox virus DNA levels**: Change from baseline in monkeypox virus DNA concentration in throat swabs at Days 7, 14, 21, 28
- (iii) **Number (%) of patients admitted to hospital for a complication of mpox** (overall and by type)
- (iv) **Time to sustained absence of use of analgesia**, defined as time to consistently reporting no use of analgesia, up to 28 days after randomisation.

Justification of trial endpoints: To date there have been no studies of mpox therapeutics in humans to inform the design of the present trial and there is little clinical experience of their use in non-hospitalised patients. As such, there are no standards for study endpoints.

[figure not shown]
Mpox lesions are painful and are known to contain high concentrations of monkeypox virus. Therefore, lesion status is both a clinically relevant outcome and an epidemiologically relevant proxy for infectiousness. Self-reported assessment of skin and mucosal lesions can be done daily, allowing a time-to-event analysis.

Primary and secondary endpoints were largely informed by subject matter experts with experience treating mpox and secondary analysis of data generated from an observational study of mpox patients in DRC carried out by the DRC's Institut National pour la Recherche Biomedicale ("National Institute for Biomedical Research" - INRB) in collaboration with the United States Army Medical Research Institute of Infectious Diseases (USAMRIID) between 2007 and 2011.[\(22\)](#) Note, however, that these data are from mpox caused by the Congo Basin clade, which is generally thought to be more severe than the West African clade, which is the cause of the current outbreak outside of Africa.

Data from the Democratic Republic of Congo suggest that the median time to all lesions being scabbed or desquamated is around study day 9, with around 77% having all lesions scabbed or desquamated by day 22 (see Figure 1). This provides sufficient data to estimate sample size requirements.

Although all lesions being scabbed or desquamated likely indicates less infectivity than active lesions, scabs do contain virus and all lesions healed (all scabs have dropped off, and intact skin remains underneath) is a more complete measure of lack of infectivity. Therefore, complete resolution of lesions will be a key secondary outcome.

Figure 1. Time to lesion resolution among a cohort of 228 patients with laboratory-confirmed mpox in the 2007-2011 INRB/USAMRIID observational study *

Time to loss of infectiousness is best assessed by conducting viral culture of daily lesion and throat swabs. However, daily swabbing is not likely to be feasible in the outpatient setting due to logistical and infection control constraints on collecting, transporting and testing such a large volume of monkeypox virus specimens. Therefore, swabbing will be intermittent, with interval censored statistical analysis.

Pain, sometime severe, is very commonly reported in clade 3 associated mpox and pain management is a major reason for admission to hospital. Therefore, alleviation of pain is an important outcome for patients.

2.4.4 Safety assessments

To evaluate the safety and tolerability of tecovirimat relative to placebo in patients with mpox:

- (i) Number (%) of patients suffering serious adverse events (overall and by type) within 28 days of randomisation
- (ii) Number (%) of patients suffering adverse events of special interest (overall and by type) within 28 days of randomisation
- (iii) Number (%) of patients suffering death, overall and by cause

2.4.5 Exploratory analyses

Other analyses may be conducted to explore the effects of tecovirimat vs. placebo on clinical efficacy, safety and microbiological outcomes, including in subsets of patients defined by baseline characteristics and medical history (with appropriate caution in the interpretation of the exploratory nature of these analyses and the multiple number of such comparisons).

2.5 Statistical analysis

A more detailed statistical analysis plan will be developed by the investigators and published on the study website whilst still blind to any analyses of aggregated data on study outcomes

by treatment allocation. All analyses for reports, presentations and publications will be prepared by statisticians and data management staff at University of Oxford.

2.5.1 Methods of analysis

Comparisons will be made between all participants randomised to the different treatment arms, irrespective of whether they received their allocated treatment (“intention-to-treat” analyses).

Primary and first secondary outcome: For time-to-event analyses of the primary and first secondary outcome, the tecovirimat group will be compared with the placebo group using a stratified log-rank test (days since symptom onset ≤ 7 , >7 days). Kaplan-Meier estimates for the time to event will also be plotted (with associated log-rank p-values). The log-rank ‘observed minus expected’ statistic (and its variance) will also be used to estimate the average event rate ratio (and its confidence interval) for those allocated to treatment group versus the placebo group.

Other secondary outcomes: Time to consistently negative culture for monkeypox virus on throat swab and on swab of most recent active skin or mucosa lesion at Days 7, 14, 21, and 28 will be analysed using an interval censored Weibull model. A negative culture will be considered ‘consistently negative’ if it is not followed by a positive culture on the same type of swab during subsequent assessments.

Subsidiary and safety outcomes: Clinical status on an ordinal scale will be compared between tecovirimat and placebo groups using a proportional odds model.⁽²³⁾ Howard’s method will be used if the proportional odds assumption is not satisfied.⁽²⁴⁾ Monkeypox virus DNA concentration will be compared between groups using the Wilcoxon rank-sum test. Data on hospital admissions and safety will be analysed using Fisher’s exact test. For time-to-event analyses of the subsidiary outcome of need for analgesia, the tecovirimat group will be compared with the placebo group using a stratified log-rank test (days since lesion onset ≤ 7 , >7 days).

Adjustment for multiple testing: A step-down approach will be used to control the family-wise error rate across the primary and three secondary outcomes: Hypothesis testing will first be conducted for the primary (time to active lesion resolution). Only if the null hypothesis is rejected at a 2-tailed $p=0.0476$, confirmatory analysis of the three secondary endpoints will be performed at a 2-tailed $p=0.0476$. To account for multiplicity of testing of the three secondary endpoints, the Benjamini-Hochberg method will be used.⁽²⁵⁾ For all other assessments (including those of subsidiary, safety, and exploratory assessments and any subgroup assessments) due allowance will be made in their interpretation for multiple comparisons.

Subgroup analyses: Pre-specified subgroup analysis will be conducted for the primary outcome using the statistical test for interaction (or test for trend where appropriate) for the following: age (<18 , $\geq 18 < 40$, ≥ 40), sex, orthopoxvirus vaccination status, and time since onset of first lesion (≤ 7 days or >7 days]).

2.6 Planned sample size

For the log-rank test of the primary endpoint ‘time to active lesion resolution’, the two key determinants of power are the total number of active lesion resolution events and the treatment-to-control ratio of the rate of active lesion resolution.

Table 1 displays the power of this test for various scenarios. In total, 318 patients with lesion resolution by day 28 are needed to detect a 40% improvement in the rate of lesion resolution as measured by the rate ratio (akin to a “hazard ratio” but for a positive outcome instead of death; values greater than one indicate improved outcomes) with at least 85% power and a two-sided α of 0.05. Conservatively assuming that the observed event rate of 77% from the 2007-2011 INRB/USAMRIID observational study will apply to the combined time to event data of experimental and control groups yields a total targeted sample size of 413 participants. **A total sample size of 500 is planned** to account for one interim analysis and approximately 10% losses to follow-up.

Table 1. Number of events needed to have 80% and 85% power at $2P=0.05$ to detect an improvement in the primary outcomes.

Rate Ratio	Scenario for 80% Power ($\beta=0.20$)		Scenario for 85% Power ($\beta=0.15$)	
	Number of Events Needed	Number of Patients Needed*	Number of Events Needed	Number of Patients Needed*
1.30	457	594	522	678
1.40	278	362	318	413
1.50	191	249	219	285

* Assumes that 77% of patients will experience the event and does not account for potential dropout. In the 2007-2011 INRB/USAMRIID observational study, 77% of patients reached lesion resolution (as defined above) within 22 days.

2.7 Sample Size Re-estimation

Since the event rate is uncertain, the sample size will be reviewed and revised based on blinded data (i.e. with time to event data for the experimental and control groups combined), when about 50% of the originally planned number of participants have reached determination of the primary endpoint.

2.8 Data and safety monitoring

The study will collect information on:

- (i) **Serious Adverse Events (SAE):** A SAE is any adverse event that:
 - results in death
 - is life-threatening*
 - requires inpatient hospitalisation or prolongation of existing hospitalisation
 - results in persistent or significant disability/incapacity
 - consists of a congenital anomaly or birth defect.

The MHRA SmPC will be the source of Reference Safety information (RSI).

- (ii) **Non-serious Adverse Events (NSAE):** This includes any new symptoms reported by the participant. Participants will be specifically asked about AEs of special interest, including headache, sore eyes, cough, shortness of breath, nausea, vomiting, diarrhoea, muscle aches, joint pain.

rm "life-threatening" in the definition of "serious" refers to an event in which the participant was at risk of death at the time of the event; it does not refer to an event which hypothetically might have caused death if it were more severe

(iii) **Reasons for prematurely stopping allocated study treatment.**

These will be ascertained from the weekly review calls with the participant by a study clinician (up to day 28), and spontaneous reports from healthcare professionals caring for the participant. In addition, participants (and their parents or carers if under 16) will be provided with a dedicated 24-hour phone support line for any trial-related queries, and with a wallet card containing details of the trial that they should carry with them during the 28 day follow-up period. These safety outcomes will be collected up to day 28 (i.e. 14 days after the completion of study treatment). Study staff that become aware of a potential SAE will report this within 24 hours to the Chief Investigator or their designee.

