Safety: All adverse events, and reasons for stopping study treatment will be recorded and will be reviewed by medical staff at the Central Coordinating Office. Suspected Unexpected Serious Adverse Reactions (SUSARs) to study medication (e.g., Stevens-Johnson syndrome, anaphylaxis, aplastic anaemia, etc.) will be reported in an expedited fashion.

Data collection: To facilitate patient isolation and infection control, and participation by clinicians and patients, data collection and all other trial procedures are streamlined and focused on those aspects critical to participant safety and the reliability of the study results. Informed consent, randomisation and follow up will be conducted remotely by telephone call or video call and data will be recorded by electronic methods by participants and trial staff.

Numbers to be randomised: The rates of clinical and microbiological resolution are uncertain for mpox in general, and in particular for the current epidemiological context.

Sample size estimates using data on the natural history of clade 1 (Congo Basin clade) mpox indicate that randomisation of 500 individuals would provide at least 85% power and a two-sided α of 0.05 to detect a 40% improvement in the rate of lesion resolution at day 28 (account for one interim analysis and approximately 10% losses to follow-up). Monitoring of blinded event rates will be used to re-estimate sample size requirements as data from the trial accrue.

Study organisation: The study is led by researchers at the University of Oxford (the regulatory trial sponsor) and includes experts in infectious disease at the Pandemic Sciences Institute and experienced clinical trialists applying methods established in the RECOVERY and PANORAMIC trials of treatments for COVID-19. Chelsea and Westminster Hospitals NHS Trust is providing sexual health expertise. The University of Liverpool is providing laboratory expertise. The study is coordinated by the Clinical Trial Service Unit in the Nuffield Department of Population Health.

To enquire about the trial, contact the PLATINUM Central Coordinating Office

PLATINUM Central Coordinating Office:
Nuffield Department of Population Health
[name]
[name]
[name]
[name]
United Kingdom

Tel: TBC
Email: TBC

Website: TBC

Table of contents

1 BACKGROUND AND RATIONALE 5

1.1 MPOX 5

1.2 TREATMENT OPTIONS..... 5

1.3 DESIGN CONSIDERATIONS 6

2 STUDY DESIGN..... 8

2.1 STUDY AIMS 8

2.2 ELIGIBILITY..... 8

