2.9 Central assessment of SAEs and onward reporting of SUSARs

All serious adverse events (SAEs) will be documented and their causal relationship to the study treatment will be assessed by the Chief Investigator or designee. Serious Adverse Events that are believed with a reasonable probability to be due to the study treatment will be considered a Suspected Serious Adverse Reaction (SSAR) (https://database.ich.org/sites/default/files/E2A_Guideline.pdf).

Clinicians at the Central Coordinating Office are responsible for expedited review of reports of SSARs received. Additional information (including relevant medical and medication history) will be sought from relevant healthcare teams. An assessment made of whether the event is “expected” or not (assessed against the relevant Reference Safety Information*). Any SSARs that are not expected would be considered a Suspected Unexpected Serious Adverse Reaction (SUSAR).

All confirmed SUSARs will be reported to the Chair of the DMC, the trial sponsor, and to MHRA and the ethics committee, in an expedited manner in accordance with regulatory requirements.

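### The serious adverse event definition has no medically-important-event criterion, so an important suspected reaction that is not life-threatening, disabling or admitted has no stated expedited route

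*Protocol*

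**What the plan says.** Protocol section 2.8 calls an adverse event serious if it "results in death", "is life-threatening", "requires inpatient hospitalisation or prolongation of existing hospitalisation", "results in persistent or significant disability/incapacity" or "consists of a congenital anomaly or birth defect". A footnote limits the second criterion: the term "refers to an event in which the participant was at risk of death at the time of the event", and an event that could have been fatal only in a worse form does not qualify. The list ends there. Other events fall into a second class, non-serious adverse events, which takes in any new symptom a participant reports.

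Section 2.9 then works on the serious class: "All serious adverse events (SAEs) will be documented and their causal relationship to the study treatment will be assessed". A serious event thought with reasonable probability to be caused by treatment becomes a suspected serious adverse reaction (SSAR). An SSAR that is not expected becomes a SUSAR. Confirmed SUSARs go in an expedited manner to the DMC chair, the sponsor, the MHRA and the ethics committee.

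The Safety paragraph of the protocol Summary illustrates SUSARs by diagnosis: "e.g., Stevens-Johnson syndrome, anaphylaxis, aplastic anaemia, etc.) will be reported in an expedited fashion". The same paragraph says that medical staff at the Central Coordinating Office will review all adverse events.

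The SAP does not define seriousness. Its section 2.6.4(i) counts patients with serious adverse events, as protocol section 2.4.4(i) does.

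**The concern.** The seriousness definition is the entry point to the trial's fast safety pathway, and it is a closed list. It has no criterion that lets a clinician class an event as serious because it is medically important in itself, or because intervention was needed to stop it reaching one of the listed outcomes.

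That matters more here than in a trial with clinic visits. Participants are managed at home, contact is remote, and children of at least 13 kg are eligible although section 2.2.4 says the drug has not been studied in paediatric trials. At stake are the speed with which an important suspected reaction reaches the Chief Investigator, whether it is assessed for causality, whether the sponsor and regulator hear of it promptly, and whether it enters the serious-event comparison between arms.

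**Working it through.** No arithmetic applies; the check is a reading of the definition against each step that uses it.

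**Step 1: count the criteria.** Section 2.8 has five. None rests on a judgement of medical importance, and no such criterion appears elsewhere in either document. Only one of the five mentions admission. Danger to life and persistent or significant disability can both be met at home.

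**Step 2: trace what depends on the definition.**

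| Step | Where | Applies to |
|---|---|---|
| Report to the Chief Investigator or designee within 24 hours | Protocol 2.8 | Potential serious events |
| Causality assessment | Protocol 2.9 | Serious events |
| SSAR, then SUSAR | Protocol 2.9 | Serious events judged related, then those not expected |
| Expedited report outside the trial team | Protocol 2.9 | Confirmed SUSARs |
| Unblinding when an SSAR is reviewed | Protocol 2.11 | SSARs |
| Serious-event outcome | Protocol 2.4.4(i), SAP 2.6.4(i) | Serious events |

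An event outside the five criteria has no stated entry to any row. The other ground for unblinding in 2.11, where allocation could change immediate medical management, stays open to it.

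**Step 3: test the definition on cases.** The clinical facts in both cases are assumed for illustration.

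- *A single seizure, assessed in an emergency department and sent home.* Section 2.2.6 says the drug's effect on seizure threshold is unknown, and Appendix 1 records an abnormal EEG change among the discontinuations in the phase 3 safety trial. If the participant was not at risk of death at the time, was not admitted and had no lasting disability, none of the five criteria is met and the event is non-serious.
- *Aplastic anaemia found early and managed without admission.* If it is neither life-threatening at the time nor disabling, it too meets none of the five. Under 2.9 it then cannot become a SUSAR, although the Summary lists that diagnosis as an example of one.

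**Step 4: see where such an event would be tabulated.** SAP section 4.1.4 covers SSARs, SUSARs, deaths, adverse events of special interest and reasons for stopping study drug. The special-interest list in SAP 2.6.4 contains no seizure, severe skin reaction or blood disorder. An event of this kind that did not lead to stopping treatment would therefore appear in none of the tables named there. It could still be looked at in exploratory analyses, and nothing prevents the DMC from asking for it.

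**The case against.** The strongest reply is that the safety net is wider than the definition, and much of that stands. The Summary provides for medical review of every adverse event. The 24-hour duty covers a potential serious event, so staff need not settle the classification before reporting. There is a 24-hour telephone line, a daily diary, weekly clinical calls and spontaneous reporting by treating clinicians. The Summary's named examples show that the authors mean such reactions to be expedited. What remains is that the review of all adverse events has no stated timeline, causality step or onward report, and that intent shown by example in a summary does not change the operative list in section 2.8.

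Several stronger readings are tempting, and the documents do not support them.

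- *That any grave reaction managed without admission is missed.* A reaction that puts the participant at risk of death, or leaves persistent or significant disability, is serious wherever it is managed and gets every step.
- *That stopping treatment depends on the definition.* Section 3.8 lists an SSAR as one circumstance among several, including the request of the participant or their doctors for any reason.
- *That detection waits up to a week for the next scheduled call.* The daily diary and the 24-hour line provide earlier routes.
- *That the number of affected participants can be estimated.* Neither document gives a rate. Appendix 1 describes adverse events in earlier human trials as mostly mild or moderate, so any assumed percentage of the 500 would have no anchor.
- *That the five-item list breaches a requirement.* The guideline linked in section 2.9 is attached to the SSAR sentence and its content is not in the documents, so this point does not rest on it.

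**Conclusion.** The point holds in a limited form. The definition has five criteria and none for medically important events. An important suspected reaction that meets none of them has no stated 24-hour report, causality assessment, SSAR or SUSAR route, or SSAR-triggered unblinding, and is not counted as serious. Section 2.8 and the Safety paragraph of the Summary also pull apart: one classifies by outcome, the other illustrates by diagnosis, and a named diagnosis can fail the outcome test.

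The size is structural. No frequency can be given, and the primary endpoint, sample size and error rates are unaffected. The conclusion assumes that staff apply the list as written and that no procedure outside these documents supplies a further criterion. It is a cheap improvement to participant protection and to the completeness of the serious-event count.

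**What to change.** Add a sixth criterion to protocol section 2.8: the event is otherwise judged medically important by the Chief Investigator or designee, because it may jeopardise the participant or need intervention to prevent one of the five listed outcomes. State that this judgement is made blind to allocation.

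Reconcile the Summary with section 2.8, so that the diagnoses given there as SUSAR examples can qualify as serious under the operative definition.

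Protocol 2.4.4(i) and SAP 2.6.4(i) need no new wording, because both count serious adverse events and will follow the revised definition. If participants have already been enrolled, screen the non-serious events on file once, blind to allocation, so that a single definition applies throughout.

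The cost is one line of protocol text, an option on the serious-event form, a few more serious-event reports and some clinical judgement in classifying them.
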